6.5.5 Post-study Therapy

There are no prohibited therapies during the post-intervention active and long-term follow-up periods. Further new anti-cancer treatment after the end of the study combination treatment will be at the discretion of the investigator. Information on at least the first new anti-cancer regimen must be recorded in the participant's source documentation, as well as in the appropriate pages of the eCRF.

At the conclusion of the study, participants who demonstrate clinical benefit may be eligible to continue to receive study treatment. They may receive further treatment, assessments and/or be followed either via a post-trial access program, a roll-over study - subject to approval by the competent health authority and ethics committee - or through any other mechanism in accordance with local legal and compliance rules. This applies to participants on study treatment and in follow-up.

Until the transition to other supportive programs, participants will continue to follow all the procedures and visits required in the current version of the protocol.

6.6 Dose Modification

Based on the known toxicity profiles of regorafenib and pembrolizumab, certain AEs are likely to be associated with one drug versus the other. For example, treatment-emergent hypertension and HFSR are likely to be associated with regorafenib rather than pembrolizumab; similarly, immune-related AEs are likely to be associated with pembrolizumab rather than regorafenib. However, some drug-related AEs such as rash, diarrhea, abnormal thyroid function, and fatigue are overlapping. Therefore, it is important to evaluate each AE and consider time of onset, perform the appropriate work-up for etiology or exclude other causes in order to determine proper management of the adverse reaction and action regarding study treatment. A careful decision should be made by investigators based on all clinical information, e.g., relatedness to study medications.

Dose modifications of regorafenib and pembrolizumab will be based on the highest grade of AE that occurred since the last contact. If a participant experiences multiple toxicities, dose modification will be based on the toxicity with the highest grade. In case of multiple toxicities of the same grade, the investigator may modify the dose based on the toxicity that appears most likely related to study interventions.

In case of dose delays, assessments should be performed on Day 1, according to the SoA (see Section 1.3).

Regorafenib dose modifications should be done according to Table 6–2.

The recommendations regarding dose adjustments and treatment interruptions from Table 6–3 to Table 6–8 can be used as support for the clinical decision and respective monitoring/ treatment guidance. A careful decision will be made by investigators based on all clinical information, e.g. relatedness to study medications.

Once a dose reduction of regorafenib has been performed, there will be no intra-participant reescalation.

Where it is indicated to reduce regorafenib one dose level, Table 6–2 should be followed:

BAY 73-4506 / 21469 08 JUN 2021

Page 59 of 141

Table 6-2: Regorafenib Dose Reduction Scheme

		Daily Regorafenib (3 weeks on, 1 week off)
Current Dose	90 mg	120 mg
Dose Level -1	60 mg	90 mg
Dose Level -2	Not applicable	60 mg

Table 6-3: Dose Modification Guidance, Non-immune Toxicities

Event	Regorafenib	Pembrolizumab
Hematologic toxicities		
G3/4 Neutropenia G3/4 Anemia G3/4 Thrombocytopenia	 Hold until recovery to ≤ G2 and reduce 1 dose level^a 1st re-appearance: Hold until recovery to ≤ G2 and reduce 1 additional dose level^a 2nd re-appearance: discontinue 	 G3 (excluding G3 neutropenia): Hold and restart at same dose if resolution to ⊆ G1 or baseline ≤ 12 weeks of last infusion Hold and consider discontinuation if NO resolution ≤ 12 weeks of last infusion G4: discontinue^b
Non-hematologic toxicities		
General guidance for G2 events	No modifications	 Consider withholding for persistent symptoms Restart at same dose if resolution to ≤ G1 or baseline ≤ 12 weeks of last infusion Consider discontinuation if NO resolution ≤ 12 weeks of last infusion^b
General guidance for G3 events	 Hold until recovery to ≤ G2 and restart at same dose level or reduce 1 dose level^a (at the investigator's discretion) 1st + 2nd re-appearance: Hold until recovery to ≤ G2 and reduce 1 dose level^a (at the investigator's discretion) 3rd re-appearance: Discontinue Discontinuation is required for gastrointestinal perforation or fistula Hold until recovery in case of cardiac ischemia and/or infarction. At the investigator's discretion restart at same dose level or reduce 1 dose level^a. Permanently discontinue if there is no resolution. 	 Hold and restart at same dose if resolution to ≤ G1 or baseline ≤ 12 weeks of last infusion Hold and discontinue if NO resolution ≤ 12 weeks of last infusion^b
General guidance for G4 events	 Hold until recovery to ≤ G2 and reduce 1 dose level 1st re-appearance: Hold until recovery to ≤ G2 and reduce 1 additional dose levela 2nd re-appearance: Discontinue Discontinuation is required for gastrointestinal perforation or fistula Hold until recovery in case of cardiac ischemia and/or 	Discontinue ^b

Table 6-3: Dose Modification Guidance, Non-immune Toxicities

Event	Regorafenib	Pembrolizumab
	infarction. At the investigator's discretion restart at same dose level or reduce 1 dose level ^a . Permanently discontinue if there is no resolution.	
Specific guidance for I	nand-foot skin reaction (HFSR)	•
G1	Maintain dose level and institute supportive measures immediately for symptomatic relief	No modification
G2	 1st occurrence: Consider decrease by 1 dose level and institute supportive measures immediately^a. If no improvement, interrupt for ≥ 7 days, until toxicity resolves or improves to G1 No improvement ≤ 7 days or 2nd occurrence: Interrupt until toxicity resolves or improves to G1. When resuming treatment, treat at reduced dose level^a. 3rd occurrence: Discontinue 	No modification
G3	 1st occurrence: Institute supportive measures immediately. Interrupt therapy for ≥ 7 days until toxicity resolves or improves to G1. When resuming treatment, decrease by 1 dose level^a. 2nd occurrence: Institute supportive measures immediately. Interrupt therapy for ≥ 7 days until toxicity resolves or improves to G1. When resuming treatment, decrease by 1 additional dose level^a. 3rd occurrence: Discontinue 	No modification
	skin and subcutaneous disorders other than HFSR (includes rash, rash	
rash macular, rash ma	culopapular, rash papular, rash pruritic, exfoliative rash, pruritus, ecze	ma, dermatitis)
G2	No modifications	 Consider withholding for persistent symptoms Restart at same dose if resolution to ≤ G1 or baseline ≤ 12 weeks of last infusion Consider discontinuation if NO resolution ≤ 12 weeks of last infusion^b

Table 6-3: Dose Modification Guidance, Non-immune Toxicities

Event	Regorafenib	Pembrolizumab
G3	 Hold until recovery to ≤ G2 and restart at same dose level or reduce 1 dose level^a (at the investigator's discretion) 1st + 2nd re-appearance: Hold until recovery to ≤ G2 and reduce 1 dose level^a (at the investigator's discretion) 3rd re-appearance: Discontinue 	 Hold and restart at same dose if resolution to ≤ G1 or baseline ≤ 12 weeks of last infusion Hold and discontinue if NO resolution ≤ 12 weeks of last infusion^b
G4 (when applicable)	 Hold until recovery to ≤ G2 and reduce 1 dose level^a 1st re-appearance: Hold until recovery to ≤ G2 and reduce 1 additional dose level^a 2nd re-appearance: Discontinue 	Discontinue ^b
Specific guidance for HYPER	rension	
G1	 No change. Consider increased BP monitoring 	No modification
G2	 If symptomatic, hold until symptoms resolve AND diastolic BP ≤ 90 mmHg. At restart, continue at the same dose level 	No modification
G3	 Hold until diastolic BP ≤ 90 mm Hg, and if symptomatic, until symptoms resolve. At restart, continue at the same dose level If BP is not controlled with the addition of new or more intensive therapy, reduce by 1 dose level^a If G3 hypertension recurs despite dose reduction and antihypertensive therapy, reduce another dose level^a 	No modification
G4	Discontinue	Discontinue ^b

BP = blood pressure; G1/2/3/4 = Grade 1/2/3/4; HFSR = hand-foot skin reaction; QD = every day

a: If reductions are required resulting in a dose of less than 60 mg QD of regorafenib, then regorafenib will be permanently discontinued. For Grade 3 neutropenia, the participant could stay on regorafenib for the first appearance, or hold until resolved to Grade 2 or less, restart at the same dose level or lower after discussion between the investigator and the sponsor.

b: After consultation with the sponsor, if toxicity is considered at least possibly related to pembrolizumab.

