Event	Regorafenib	Pembrolizumab	
Specific guidance for IMMUNE-	RELATED ADVERSE EVENTS		
General instructions concerning	g pembrolizumab:		
	1. Severe and life-threatening irAEs should be treated with IV corticosteroids followed by oral steroids. Other immunosuppressive treatment should		
begin if the irAEs are not	controlled by corticosteroids.		
Pembrolizumab must be j	permanently discontinued if the irAE does not resolve or the cort	ticosteroid dose is not ≤10 mg/day within 12 weeks of the	
last pembrolizumab treatr	ment.		
The corticosteroid taper s	hould begin when the irAE is ≤ Grade 1 and continue at least 4	weeks.	
4. If pembrolizumab has bee	en withheld, pembrolizumab may resume after the irAE decrease	ed to ≤ Grade 1 after corticosteroid taper.	
Pneumonitis	 G2 or higher: Interrupt until ≤ G1 	G2: Withhold	
 Monitor participants for 	 Restart at same dose level for G2 and decrease by 	Recurrent G2, G3, or G4: Permanently discontinue	
signs and symptoms of	1 dose level for G3/4 ^a	Administer corticosteroids (initial dose of 1-2 mg/kg	
pneumonitis		prednisone or equivalent) followed by taper: add	
 Evaluate participants with 		prophylactic antibiotics for opportunistic infections	
suspected pneumonitis with			
radiographic imaging and			
initiate corticosteroid			
treatment			

Table 6–7: Dose Modification Guidance, Other Immune-related Adverse Events

Event	Regorafenib	Pembrolizumab
Specific guidance for IMMUNE	-RELATED ADVERSE EVENTS	
New onset Type 1 Diabetes Mellitus (T1DM) or G3 or G4 hyperglycemia associated with evidence of β-cell failure • Monitor participants for hyperglycemia or other signs and symptoms of diabetes	• Interrupt until ≤ G1. Restart at same dose level.	 Withhold^b Initiate insulin replacement therapy for participants with T1DM Administer anti-hyperglycemic in participants with hyperglycemia
 Hypophysitis Monitor for signs and symptoms of hypophysitis (including hypopituitarism and adrenal insufficiency) 	• Interrupt until ≤ G1. Restart at same dose level.	 G2: Withhold G3/4: Withhold or discontinue (at the investigator's discretion)^b Administer corticosteroids and initiate hormonal replacements as clinically indicated
Monitor for signs and symptoms of thyroid disorders	 G2: No modifications G3/4: Interrupt until ≤ G2. Restart at same dose level. 	 G2: Continue G3/4: Withhold or discontinue (at the investigator's discretion)^b Treat with non-selective beta-blockers (e.g. propranolol) or thionamides as appropriate

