 Hypothyroidism Monitor for signs and symptoms of thyroid disorders 	 No modification Initiate thyroid replacement hormones (e.g. levothyroxine or liothyronine) per standard of care 	 Continue Initiate thyroid replacement hormones (e.g. levothyroxine or liothyronine) per standard of care
Monitor changes of renal function; grading according to increased creatinine or acute kidney injury	 G2: Continue G3/4: Interrupt until ≤ G2. Restart at same dose level. 	 G2: Withhold G3/4: Permanently discontinue Administer corticosteroids (prednisone 1-2 mg/kg or equivalent) followed by taper
Neurological toxicities	 G2 or higher: Interrupt until ≤ G1 Restart at same dose level for G2 and decrease by 1 dose level for G3/4a 	 G2: Withhold G3/4: Permanently discontinue Based on severity of AE administer corticosteroids

Table 6–7: Dose Modification Guidance, Other Immune-related Adverse Events

Event	Regorafenib	Pembrolizumab
Specific guidance for IMMUNE	RELATED ADVERSE EVENTS	
Myocarditis Ensure adequate evaluation to confirm etiology and/or exclude other causes	 G2 or higher: Interrupt until ≤ G1 Restart at same dose level for G2 and decrease by 1 dose level for G3/4^a 	 Grade 1: Withhold Grade 2/3/4: Permanently discontinue Based on severity of AE administer corticosteroids
Exfoliative dermatologic conditions	 Suspected Steven-Johnson Syndrome (SJS), toxic epidermal necrolysis (TEN), or drug rash with eosinophilia and systemic symptoms (DRESS): Withhold Confirmed SJS, TEN, or DRESS: Permanently discontinue Based on severity of AE administer corticosteroids Ensure adequate evaluation to confirm etiology or exclude other causes 	 Suspected SJS, TEN, or DRESS: Withhold Confirmed SJS, TEN, or DRESS: Permanently discontinue Based on severity of AE administer corticosteroids
All other immune-related AEs (e.g. immune-mediated arthritis, pancreatitis, uveitis, etc.) • Ensure adequate evaluation to confirm etiology or exclude other causes	 G2 or higher: Interrupt until ≤ G1 Restart at same dose level for G2 and decrease by 1 dose level for G3/4^a 	 Persistent G2: Withhold G3: Withhold or discontinue based on the event^c Recurrent G3 or G4: Permanently discontinue Based on severity of AE administer corticosteroids

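### Section 6.6 lets the single highest-grade toxicity set the dosing of both drugs; read literally, Grade 3 hand-foot skin reaction or hypertension displaces a pembrolizumab stop or withhold row for a lower-grade event

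*Protocol*

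**What the plan says.** Protocol Section 6.6 gives two general rules. The first covers both drugs: "Dose modifications of regorafenib and pembrolizumab will be based on the highest grade of AE that occurred since the last contact". The second covers coinciding events: "If a participant experiences multiple toxicities, dose modification will be based on the toxicity with the highest grade". A third sentence lets the investigator pick the event most likely related to study treatment, but only among toxicities of equal grade.

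The same section also contains softer text. Before the rules it attributes HFSR and hypertension mainly to regorafenib and immune-related events mainly to pembrolizumab, and says "it is important to evaluate each AE and consider time of onset". After them it says that the recommendations in Tables 6-3 to 6-8 "can be used as support for the clinical decision", with a careful investigator decision on all clinical information, relatedness included.

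The tables have a row for each event and grade, and a separate column for each drug.

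**The concern.** A highest-grade rule is safe only if a higher grade of any event always brings an action at least as strict as a lower grade of any other event. For pembrolizumab that does not hold. Some Grade 3 events that the protocol itself links to regorafenib leave pembrolizumab untouched, while several Grade 1 or Grade 2 immune-related events require it to be withheld or stopped. When two such events coincide, the rule as written selects the Grade 3 row and so gives a less safe pembrolizumab action than the other event's own row. The tie-break cannot help, because the grades differ.

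The individual events are foreseeable. Section 4.3 reports Grade 3 HFSR among the dose-limiting toxicities in the Phase 1b study of this combination, and Section 6.6.1 says diarrhea could be very common. How often they coincide is not given.

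**Working it through.** No arithmetic applies. The check sets the pembrolizumab column of the tables against the rule in Section 6.6.

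**Higher-grade rows that leave pembrolizumab alone (Table 6-3)**

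- Grade 3 HFSR: "No modification".
- Grade 3 hypertension: the same entry.

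**Lower-grade rows with a stricter pembrolizumab action (examples, not a full list)**

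| Event | Table | Pembrolizumab action |
|---|---|---|
| Myocarditis, Grade 2 | 6-7 | Stop: "Grade 2/3/4: Permanently discontinue" |
| Pneumonitis, recurrent Grade 2 | 6-7 | Stop: "Recurrent G2, G3, or G4: Permanently discontinue" |
| Myocarditis, Grade 1 | 6-7 | "Grade 1: Withhold" |
| Pneumonitis, first Grade 2 | 6-7 | Withhold |
| Hypophysitis, Grade 2 | 6-7 | Withhold |
| Renal toxicity, Grade 2 | 6-7 | Withhold |
| Neurological toxicity, Grade 2 | 6-7 | Withhold |
| Diarrhea, Grade 2 | 6-4 | Withhold |

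**Worked cases under the literal rule**

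1. Grade 3 HFSR with Grade 2 myocarditis. HFSR has the higher grade and governs, so pembrolizumab is unchanged. The myocarditis row says stop.
2. Grade 3 hypertension with Grade 2 pneumonitis. Hypertension governs, so pembrolizumab is unchanged. The pneumonitis row says withhold, or stop if recurrent.
3. Grade 3 HFSR with Grade 2 diarrhea. HFSR governs, so pembrolizumab is unchanged. The diarrhea row says withhold.

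**Is the conflict resolved elsewhere?** No section says to apply the rule drug by drug or to take the strictest action for each drug. Section 7.1.1.3 lists unacceptable pembrolizumab toxicity only under reasons for which a participant may be withdrawn, and defines it by reference back to Section 6.6. For regorafenib, Section 7.1.1.2 makes withdrawal mandatory for an event whose guidance calls for permanent discontinuation.

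**Rows the rule cannot rank.** Several rows in Table 6-5 are triggered by laboratory thresholds, Child-Pugh score or clinical events such as new ascites, not by a toxicity grade. A highest-grade comparison does not order them against other events.

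**Effect on the analysis.** The decision rules in Section 9.2 (27 of 93 and 34 of 119 responders) do not depend on this text. In the worked cases the Grade 3 event already interrupts or holds regorafenib, so the number of participants with any dose modification should not change. Only the drug-specific interruption and discontinuation tables in SAP Section 5.4.1.2 could shift.

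**The case against.** The strongest reply is that the conflict appears only if two sentences are taken out of their section. The text around them assigns events to drugs, asks for each event to be evaluated, and leaves the decision to the investigator on all clinical information. An entry of no modification in the HFSR row most naturally means that HFSR itself does not call for a pembrolizumab change, not that it cancels another event's row. Section 6.6.3 ties withholding or stopping pembrolizumab to the severity of the immune-related event. Section 6.6.5 says the guidance applies when the event is judged related to pembrolizumab. Section 7.1.1.1 requires withdrawal where the investigator considers continuation harmful.

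This stands as a reason to expect sensible dosing. It does not cure the wording: the highest-grade sentences are phrased as what will be done, while the table rows that would correct them are offered only as support.

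Two further points also stand:

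- A reader might infer that regorafenib is equally exposed, because a third Grade 2 HFSR calls for discontinuation while several Grade 3 rows allow restart at the same dose. Section 7.1.1.2 largely covers this, since it is mandatory and framed by event.
- A reader might add the Grade 2 infusion reaction despite premedication as an example. It is weak: Table 6-8 has it managed at the bedside by stopping the infusion, and a rule about grades since the last contact would hardly govern it.

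Finally, deleting both highest-grade sentences would be a mistake. The first also makes the worst grade since the last contact count. Without it, Grade 3 diarrhea that had improved to Grade 1 by the visit could be read on the Grade 1 row, which changes neither drug.

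**Conclusion.** The point holds as a wording defect in a safety rule, mainly on the pembrolizumab side. Followed literally, Section 6.6 gives a less safe pembrolizumab action than the lower-grade event's own row in the cases shown. It should be corrected because it is a stated rule that points the wrong way, not merely a missing detail.

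Its size cannot be given as a number. The documents do not say how often Grade 3 HFSR or hypertension coincides with one of the listed events, and no count of conflicting row pairs is claimed.

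Two stronger readings are tempting. One is that sites would keep giving pembrolizumab to participants with myocarditis or pneumonitis. The documents do not support this, because the judgement and attribution text makes such an error unlikely. The other is that the efficacy result is at risk. It is not: ORR, alpha and power are untouched.

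The conclusion assumes the sentences are read as written. The SAP version history records that recruitment stopped early, so the practical benefit lies with anyone still on treatment or in continued access, and with any reuse of this text.

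**What to change.** Keep the worst-grade principle, but apply it to each event. Reword the first sentence along these lines: *For every toxicity, the worst grade reached since the previous contact selects its row in Tables 6-3 to 6-8.*

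Replace the multiple-toxicity sentence and the equal-grade tie-break with: *Where toxicities coincide, each is considered separately for regorafenib and for pembrolizumab, and the most restrictive applicable action for that drug is followed, subject to the investigator's attribution and clinical judgement.*

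Add that rows in Table 6-5 set off by laboratory thresholds, Child-Pugh score or clinical events are applied by their own trigger. The tables keep their status as support for the clinical decision.

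The cost is a few sentences in one section, with no extra participants, visits, data or analyses. The small downside is somewhat more interruptions of one drug when events coincide.

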6.6.1 Dose Modification and Management of Lower Gastrointestinal Toxicity

Gastrointestinal (GI) toxicity in the form of diarrhea could be very common and a potentially serious event caused by regorafenib and pembrolizumab combination therapy, as both regorafenib and pembrolizumab may cause gastrointestinal adverse reactions. Diarrhea could be either the only presenting symptom of GI toxicity, potentially self-limiting, or part of immune checkpoint inhibitor-induced colitis that could require hospitalization and intensive treatment. Immune-related colitis (any grade) has been reported in 1.8% of patients receiving pembrolizumab. The median time to onset of immune-related colitis was 3.5 months whereas the median duration was 1.4 months, leading to discontinuation of pembrolizumab in 0.5% of patients. No predictive marker for the occurrence of gastrointestinal toxicity related to immune checkpoint inhibitors has been validated yet. As such, it is important to distinguish among different types of diarrhea and exclude alternative etiology (e.g. disease progression, other medications, infections).

Table 6-4: Dose Modification Guidance, Lower Gastrointestinal Toxicity

General instructions for management of lower gastrointestinal toxicity:

- Monitor all participants for signs and symptoms of enterocolitis (i.e. diarrhea, abdominal pain, blood or mucus in stool with or without fever) and bowel perforation (i.e. peritoneal signs and ileus)
- For diarrhea G1 and G2:
 - o Oral fluids, loperamide, avoid high fiber/lactose diet
 - For diarrhea G2 (> 7 days) or higher, consider per local institutional guidelines:
 - o Blood tests (e.g. hematology and general chemistry including liver function tests (AST, ALT, Bilirubin))
 - o Stool (e.g. culture, Clostridium difficile, cytomegalovirus (CMV) or other viral etiology, ova, and parasite)
 - o GI consultation and imaging (e.g., CT scan of abdomen and pelvis and GI endoscopy with biopsy)
 - Administer corticosteroids (initial dose of 1-2 mg/kg prednisone or equivalent) followed by taper upon AE improving to ≤ G1 and continue to taper over at least 4 weeks
- For severe and life-threatening diarrhea and/or immune-related colitis:
 - o Consider hospitalization or outpatient facility for participants with dehydration or electrolyte imbalance
 - o Fluid and electrolytes should be administered via IV infusion
 - o Urgent GI consultation and imaging (e.g., CT scan of abdomen and pelvis and GI endoscopy with biopsy)
 - IV corticosteroid should be initiated first followed by oral steroid. Other immunosuppressive treatment should be initiated if irAEs cannot be controlled by corticosteroids

Event	Regorafenib	Pembrolizumab
Diarrhea G1; <4 stools/day over baseline	No modifications	No modifications
Diarrhea G2; 4-6 stools/day over baseline	No modifications, BUT if diarrhea G2 persistent	G2: Withhold; restart at same dose if
	(not back to ≤ G1 in 7 days), hold regorafenib until	resolution to ≤ G1 or baseline ≤ 12 weeks of

Table 6–4: Dose Modification Guidance, Lower Gastrointestinal Toxicity
--

	back to ≤ G1. Restart at same dose level or reduce 1 dose level ^a (at the investigator's discretion).	last infusion and corticosteroid has been tapered
Diarrhea G3; ≥7 stools/day over baseline	G3: Hold regorafenib until back to ≤ G1. Restart at same dose level or reduce 1 dose level ^a (at the investigator's discretion)	 G3: Withhold; restart at same dose if resolution to ≤ G1 or baseline ≤ 12 weeks of last infusion and corticosteroid has been tapered Recurrent G3: permanently discontinue
Diarrhea G4; Life-threatening consequences	G4: Interrupt until ≤ G1. Restart at one dose level below ^a	G4: Permanently discontinue

AE = adverse event; ALT = alanine aminotransferase; AST = aspartate aminotransferase; CMV = cytomegalovirus; CT = computed tomography; G1/2/3/4 = Grade 1/2/3/4; GI = gastrointestinal; IV = intravenous; irAE = immune-related adverse event; QD = every day a: If reductions are required resulting in a dose of less than 60 mg QD of regorafenib, then regorafenib will be permanently discontinued.

